4.3. Study procedures

4.3.a. Subject Identification

REDCap will be used to identify and determine the eligibility of the participants who are redirected from the Facebook targeted advertisement (see 4.3.c. for description of Facebook targeted advertisement). REDCap will also be utilized for the consent process and to randomize the participants. Once the participant is randomized, the study team will register the participant in CTMS.

4.3.b. Data for Identification

A screening form to confirm eligibility will be completed prior to completion of the baseline survey and randomization to intervention arm. The screening survey will assess:

- Age 50-80 years;
- ≥20-pack-year smoking history;
- Individuals who currently smoke or quit smoking within the past 15 years;
- Previous LDCT for early detection of lung cancer, lung nodule or nodules that are currently being followed
- Has ever been diagnosed with lung cancer

4.3.c. Screening and Recruitment Process

We will use a highly successful recruitment strategy via FB Targeted Advertisement (FBTA)¹⁸ to recruit screening-eligible individuals from Indiana, Kentucky, Pennsylvania, Oklahoma, and Oregon. We chose geographically-diverse states with a 15.9% or greater adult smoking rate representing all regions of the U.S. making the plausibility of screening-eligible individuals in the area high in addition to offering racial and ethnic diversity. We have chosen FB as our social media platform for recruitment in part because, as of 2021, individuals aged 65 and older are the fastest growing demographic group on Facebook (FB). FB use in individuals born in 1945 or earlier has nearly doubled in the past three years. Further, out of the 2.7 billion FB users, over 32 million are age 50 and older – the age for lung screening eligibility.

FB has the ability to “target” an advertisement by demographics and keywords listed in each individual FB user’s profile or interest list. The FB user’s interest list includes a wide range of details a user can indicate when setting up and/or maintaining their profile that they have an

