interest in such as groups, hobbies, lifestyle choices, behaviors, points of view, specific organizations and more. This allows us to purposively sample people who are age 50 years and older, indicate smoking as an interest and reside in a particular state, city, or zip code. Using this approach, as we have in prior studies,^{9,14,17,18} we can target our advertisement on FB using the following keywords: cigarette, tobacco, nicotine replacement therapy, nicotine gum, electronic cigarette, smoking. Guided by the safety and monitoring guidelines for researchers using social media,⁴⁸ our approach includes design and close monitoring of the FBTA to ensure all methodologic and ethical standards are upheld.

We are partnering with the GO₂ Foundation to identify Lung Cancer Screening Centers of Excellence (as certified by the GO₂ Foundation)⁴⁹ to identify primary care networks to connect individuals who seek a screening referral request but do not have a primary care clinician. There are more than 600 Screening Centers of Excellence nationwide. There are 126 Screening Centers of Excellence in the 5 states in which we will conduct the proposed study. These centers are well-established, well-connected, and strong collaborators with their local primary care networks making them the ideal national partner to connect participants without a primary care clinician to one for the patient-clinician discussion about screening prior to referral. They also can link individuals to care regardless of insurance status through federally qualified health centers and community health centers fostering access to high quality screening for low income and other vulnerable subpopulations.

A screening form to confirm eligibility and baseline assessment will be completed prior to receiving the intervention.

Assessment or Measure	Screening	Baseline (T1)
Screening/eligibility Assessment	X	
Demographic and Health Status Characteristics		X
Knowledge: Lung Cancer Screening		X
Perceived Risk of Lung Cancer Scale ¹⁶		X
Perceived Benefits of Lung Cancer Screening Scale ¹⁶		X
Perceived Barriers to Lung Cancer Screening Scale ¹⁶		X
Self-Efficacy for Lung Cancer Screening Scale ¹⁶		X
Self-report of Occurrence of a Patient-Clinician Discussion about Lung Cancer Screening		X
Self-report via the stages of adoption algorithm for screening with verification process		X
Self-report of upcoming visit with primary care provider scheduled		X

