FB Analytics. Using the FB analytics component⁴⁶ of our FBTA, our assessment plan will measure the total reach of the FBTA to increase awareness of the option to screen for lung cancer among screening-eligible individuals.⁴⁷ Quantitative data collected from FB analytics during the recruitment campaign will assess reach by detailing: 1) reach; 2) link clicks; and 3) impressions.⁴⁶ Reach in FB analytics is defined as the number of people who saw the FBTA at least once.⁴⁶ This can be further analyzed by hour, day, specific number of days, week, and campaign length. In addition, reach can be further stratified by specific location (i.e., state, city, town, county, zip code).⁴⁶ Table 1 defines key Facebook analytics for this study. In addition, Facebook will provide the number of people who meet the target profile, within each location.

Table 1. Key Facebook Analytics to Assess Reach	
Facebook Analytic	Definition
Reach ⁴⁶	Total # of people who saw the FBTA at least once.
Link Clicks ⁴⁶	Total # of clicks on the link within the FBTA that led to the REDCap survey platform of the study.
Impressions ⁴⁶	Total # of times the FBTA was on screen (may include multiple views of the ad by the same person/people).

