5.7. Follow-up and end-of study (if applicable) n/a

5.8. Statistical Method

This behavioral intervention study will randomize 500 screening-eligible individuals in a 1:1 ratio into the *LungTalk* intervention or the non-tailored video intervention condition. We will use descriptive statistics such as means, standard deviations, and frequency distributions/distributional assumptions to examine data quality, identify patterns of missing and out-of-range values, and evaluate parametric assumptions. Remediation of normal distribution assumption violations will be accomplished using the Box-Cox procedure for transformations. We will apply the intention-to-treat (ITT) principle in handling missing data on screening uptake; a study participant will be coded as 'no screening uptake' unless otherwise verified by our participation sites. We will examine violations of the missing-at-random assumption for secondary outcomes. If missingness is associated with any

observed characteristics, then covariates associated with missingness will be incorporated into a sensitivity analysis to minimize bias.

Aim 1. Examine the use of a social media platform (i.e., Facebook) to reach high-risk individuals eligible for lung screening. We will describe and compare the following measures and metrics using a mixture of data from FB analytics and study data from REDCap.

Goal	Analytic Plan
Estimate the number and percentage of individuals aged 50 and older who currently or formerly smoke in the population that the advertisement is marketed.	Numerator = # of Facebook members age 50+ who currently or formerly smoke in target markets Denominator = total # of Facebook members in target markets Both numerator and denominator provided by FB Analytics.
Estimate the approximate percent of this population to which this advertisement is marketed are eligible for lung screening according to the USPSTF guidelines.	Numerator = # of eligible participants, among those screened. Denominator = total number screened. Data from screening survey.
Record the percent of eligible participants who agree to participate in the study.	Numerator = total number consented Denominator = # of eligible participants
Compare differences between those participating and those not participating on smoking status (i.e., current vs. former), age, gender, geography, and other key variables collected on the screening survey.	Descriptive tables along with a series of independent samples t-tests and Chi-square tests.

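### Aim 1, row 1: a Facebook audience count defined by age and keyword interest is labelled as a count of people who smoke or used to smoke, and the population behind the percentage is not named

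*Combined protocol and SAP*

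**What the plan says.** The Aim 1 table in section 5.8 opens with this goal: "Estimate the number and percentage of individuals aged 50 and older who currently or formerly smoke in the population that the advertisement is marketed". The numerator is "Numerator = # of Facebook members age 50+ who currently or formerly smoke in target markets" and the denominator is "Denominator = total # of Facebook members in target markets". On the source, the row adds: "Both numerator and denominator provided by FB Analytics".

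The FB Analytics part of section 5.5 lists what Facebook supplies. It names three campaign metrics (reach, link clicks, impressions) and then one population count: "Facebook will provide the number of people who meet the target profile, within each location".

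Section 4.3.c defines the profile. Advertisements are targeted "by demographics and keywords listed in each individual FB user’s profile or interest list", which lets the team "purposively sample people who are age 50 years and older, indicate smoking as an interest" in chosen locations. The keywords are "cigarette, tobacco, nicotine replacement therapy, nicotine gum, electronic cigarette, smoking".

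Section 4.1 acknowledges that Facebook users who list smoking as an interest may differ from people who qualify for screening but list no such interest. It leaves that question to future research.

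**The concern.** Row 1 presents its numerator as a count of people with a smoking history. Nothing in the protocol describes a Facebook field that records whether a member smokes or has quit. What is described is a match on age, location and listed interests. An interest match can miss people who smoke or have quit but list nothing, and it can pick up people who list a keyword without having smoked.

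Reaching high-risk people is a stated primary objective, and row 1 is the row that sizes the at-risk population on the platform. Followed as written, it would publish an advertising-audience size as the number and percentage of older members who smoke or used to smoke. The caveat in section 4.1 is not carried into the row. A reader also could not tell which population the percentage describes.

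**Working it through.** The plan gives no numerical result for this row, so there is no figure to reproduce. The check compares definitions, then asks how far the label could mislead.

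**1. Numerator: label against source**

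- Label (5.8, row 1): members aged 50 or over who smoke or used to smoke.
- Source (5.8, row 1): Facebook's analytics, not the study's survey.
- Population count described (5.5): people matching the target profile, by location.
- Profile (4.3.c): age 50 or over plus a listed interest. None of the six keywords records current or former smoking.

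Row 1 does not itself say that the count is a keyword match. That is an inference, but the documents describe no other source for the number.

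**2. Can the error be sized?**

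Let p be the share of members aged 50 or over who smoke or used to smoke, Se the proportion of them whom the keywords catch, and f the proportion of never-smokers who also match. Then:

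matched share = p × Se + (1 − p) × f

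The documents give none of the three. The values below are assumptions that only illustrate the range.

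| p | Se | f | Matched share of members 50+ |
|---|---|---|---|
| 50% | 5% | 0% | 0.50 × 0.05 = 2.5% |
| 50% | 50% | 2% | 0.25 + 0.01 = 26% |
| 50% | 100% | 10% | 0.50 + 0.05 = 55% |
| 30% | 5% | 0% | 0.30 × 0.05 = 1.5% |
| 30% | 100% | 10% | 0.30 + 0.07 = 37% |

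The matched share is too low when p(1 − Se) exceeds (1 − p)f and too high when the reverse holds. Neither direction can be excluded from the documents.

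**3. Denominator: three readings of the goal**

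- *All members in the geographic markets.* The written denominator fits, and the numerator is nested in it. The mislabelled numerator remains.
- *Members aged 50 or over.* The written denominator does not fit, because it has no age limit.
- *The audience actually targeted.* The available numerator and the base are then the same people, so the ratio is 100% by construction.

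No reading yields a percentage of people who smoke or used to smoke while the numerator is an interest match.

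**4. How much the choice of base changes the number**

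The background (section 2.1) says that 30.8% of 226 million US users are aged 50 or over. Assume that this national share holds in the target markets. Then:

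percentage of all members = 0.308 × percentage of members 50+

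The two differ by a factor of 1/0.308 = 3.25. With a perfect numerator, an assumed 30% to 50% of members 50+ becomes 9.2% to 15.4% of all members. The 30.8% should be used with care: it implies 0.308 × 226 million = 69.6 million users aged 50 or over, whereas section 4.3.c gives a figure of just over 32 million.

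**The case against.** The strongest case against the point has three parts.

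**The denominator is defensible.** A reader might infer that dividing by members of every age is an error that shrinks the percentage about 3.2-fold. The documents do not support that. Markets are naturally read as places: section 4.3.c names states, and section 5.5 speaks of counts by location. On that reading, older members who smoke or used to smoke, over all members there, is the percentage the goal asks for. The factor of 3.25 is then a ratio between two legitimate percentages with different bases, not a bias. What stands is that the goal's wording permits other bases and the plan does not choose.

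**Aim 1 does not rest on row 1.** A reader might also infer that the conclusion about who is reached would be wrong. That does not follow. Reach, link clicks and impressions are separate metrics. Row 2 takes the eligible share from the screening survey, and row 4 compares participants with non-participants on smoking status. None of these uses the row 1 count.

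**The numerator problem is inferred and partly disclosed.** Row 1 never says keyword match, section 5.5 does not say that the profile count is the only one available, and section 4.1 admits the limitation. That is fair, but it does not rescue the label. No smoking-status count is described anywhere, and an acknowledgement in the design section does not turn an interest match in the analysis table into smoking status.

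**Conclusion.** The point holds for the label and, more weakly, for the base. Row 1 as written would report an advertising-audience count as a count of people who smoke or used to smoke. This rests on one assumption: that the Facebook count meant in row 1 is the target-profile count of section 5.5, the only such count described. The error could be large and could run either way. It has no determinable size, because the documents say nothing about how keyword interest relates to smoking history.

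The denominator is ambiguous, not shown to be wrong. The choice of base changes the reported percentage by a factor of about 3.25, if the national 30.8% applies in the target markets.

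The consequence is confined to one descriptive row under a primary aim. No hypothesis test, power figure, randomised comparison or primary outcome uses it. It should be corrected because the published number would otherwise be mislabelled and the correction is cheap.

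**What to change.** - Relabel the numerator as Facebook members aged 50 or over matching the targeting profile, and drop the claim that it counts people who smoke or used to smoke. Reword the row's goal to match, and carry the section 4.1 caveat into the row.
- Name the denominator population. Report the figure per member aged 50 or over and per all members in the target markets.
- Take any share of people who smoke or used to smoke from the screening survey, labelled as a share of self-selected screener completers. First confirm that the screener separates never-smokers from people who quit more than 15 years ago. The items listed in section 4.3.b do not show this, and both groups would simply be ineligible.

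The cost is one reworded table row, one extra age-filtered audience count and possibly a small change to a screener item. The downside is that Aim 1 makes a more modest descriptive claim about the population on the platform.

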5.4. Assignment / randomization (if applicable)

After eligibility is confirmed in REDCap, participants will be registered in the CTMS system. Upon completion of baseline assessment, participants will be randomized using the REDCap randomization module to one of the two arms (i.e., LungTalk or non-tailored GO² video) using a stratified block design stratifying by smoking status (current vs former). Stratified random assignment will ensure the two groups are comparable in distribution on smoking status, a salient variable for lung screening behavior noted in our prior work.^{9,17,41} Consolidated Reporting of Randomized Clinical Trials (CONSORT) guidelines for RCTs will be followed.

5.5. Section of instruments (to include for all studies with a social behavioral intervention)

Table 1. Measures and Timepoints of Assessment

Constructs	Assessment or Measure	# of Items	Time to Complete (min)	Validated?	Baseline (T1)	1 Wk Follow-Up (T2)
Eligibility	Screening Survey	3	1	N		
Demographics	Demographic and Health Status Characteristics	20	5	N	X	
Knowledge	Knowledge: Lung Cancer Screening	9	5	N	X	X
Perceived Risk	Perceived Risk of Lung Cancer Scale ¹⁶	3	1	Y	X	X
Perceived Benefits	Perceived Benefits of Lung Cancer Screening Scale ¹⁶	6	3	Y	X	X
Perceived Barriers	Perceived Barriers to Lung Cancer Screening Scale ¹⁶	17	10	Y	X	X
Self-Efficacy	Self-Efficacy for Lung Cancer Screening Scale ¹⁶	9	5	Y	X	X
Occurrence of a Patient-Clinician Discussion	Self-report of Occurrence of a Patient-Clinician Discussion about Lung Cancer Screening	1	1	N	X	X
Screening Uptake	Self-report via the stages of adoption algorithm for screening with verification process	1	1	N	X	X
Upcoming PCP Visit	Self-report of upcoming visit with	1	1	N	X	X

	primary care provider scheduled				
1. Screening Survey	TOTAL TIME		32 minutes	27 minutes	

will be used to determine eligibility. See Section 4.3.b above for details.

2. **Demographic and Health Status Characteristics** will be assessed using items we have used in prior studies. These include age, gender, race/ethnicity, education level, income level, perceived financial status, insurance status, marital status, employment status, smoking status (if former, how long since quit in months), and family history of lung cancer.

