Record reasons that participants refuse to participate in the study.	Descriptive analysis from screening survey data.
Estimate attrition at 1 week and 6-month follow-up time periods.	Numerator = # of baseline participants - # of participants who complete the follow-up assessment (either 1 week or 6 month) Denominator = # of baseline participants Completion at follow-up defined as completing, at the least, the screening/stage of adoption item.
Compare differences between those completing and those not completing the study on sociodemographic and health status variables, geography, baseline scores on knowledge, lung cancer screening health beliefs, and stage of adoption for lung cancer screening.	Descriptive tables along with a series of independent samples t-tests and Chi-square tests. Completion of the study is defined as completing the screening uptake item for the 6-month assessment.

Aim 2. Compare the effectiveness of a computer-tailored health communication and decision support tool (LungTalk) to a non-tailored Lung Screening Informational Video on lung screening: 1)

knowledge; 2) health beliefs (perceived risk, perceived benefits, perceived barriers, self-efficacy); 3) occurrence of a patient-clinician discussion about lung screening; and 4) uptake and completion (primary outcome). Total knowledge scale scores and Lung Cancer Screening Health Beliefs (total scale scores for perceived risk, perceived benefits, perceived barriers, self-efficacy) are continuous variables. Occurrence of patient-clinician discussion and screening uptake are dichotomous variables. Prior to group comparisons, measures will be described by timepoint, both overall and by group. Within-group changes will be assessed using standardized effect sizes. The primary outcome is screening uptake at 6-month follow-up. For between-group comparisons, generalized linear models will be used with adjustment for smoking status; appropriate link functions for each outcome will be determined based on distributions (e.g., for dichotomous outcome variables we will use a logit link). In the case of differential attrition, as noted above, a sensitivity analysis will be conducted such that regression models will also include baseline covariates that differ significantly between participants who do and do not complete follow-up assessments.

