5.8.1. Sample size calculation and justification

With a sample size of n=250 per group and up to 20% missing assessment data (n=200 available for analysis) on total knowledge scale and total perceived risk scale scores (secondary outcomes), we will have an 80% statistical power if the difference is d=0.28 (in standardized effect size units, or Cohen d), in an independent-sample t-test with a two-sided type-I error rate of 5%. A 0.25 effect is what Cohen considered a 'small' effect size in psychology research, thus a conservative estimate of the statistical evidence that can be supported in our study design.

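### Secondary continuous outcomes: naming the baseline score as a covariate in the main Aim 2 models would gain precision at no cost (with a minor wording slip on the 0.25 effect in 5.8.1)

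*Combined protocol and SAP*

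**What the plan says.** Aim 2 in section 5.8 treats the knowledge total and the four health-belief totals ("total scale scores for perceived risk, perceived benefits, perceived barriers, self-efficacy") as continuous outcomes. For comparing the arms, "generalized linear models will be used with adjustment for smoking status", with the link chosen by the outcome's distribution. Smoking status is the stratification factor in 5.4. No baseline score is named for these main models, and none is expressly excluded.

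Table 1 in 5.5 marks all five scores at baseline (T1) and at follow-up. Section 5.4 fixes the order: "Upon completion of baseline assessment, participants will be randomized using the REDCap randomization module". The baseline scores are therefore true pre-randomization measurements.

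Other baseline covariates enter only in a sensitivity analysis, when attrition is differential. In that case "regression models will also include baseline covariates that differ significantly between participants who do and do not complete follow-up assessments".

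Section 5.8.1 gives power for two of the five scores, knowledge and perceived risk. It allows for "up to 20% missing assessment data (n=200 available for analysis" per group) and states that "we will have an 80% statistical power if the difference is d=0.28", "in an independent-sample t-test with a two-sided type-I error rate of 5" per cent. It then describes a 0.25 effect as a small "effect size in psychology research, thus a conservative estimate of the statistical evidence that can be supported in our study design".

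**The concern.** A score measured before randomization usually predicts the same score afterwards. Including it in the model removes that part of the residual variance, so the same participants give a narrower confidence interval for the arm difference. The plan collects these scores but does not say that the main comparisons will use them. The attrition analysis does not fill the gap. It addresses bias from missing data, is conditional, and selects covariates by their relation to dropout. A baseline score that strongly predicts its own follow-up value but not dropout would never enter. Because the plan neither includes nor excludes the baseline score, the covariate set also stays open until results are available.

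The wording in 5.8.1 is a separate, smaller matter. An effect of 0.25 is harder to detect than one of 0.28. Calling it conservative for what the design can support may lead a reader to think that it is detected with 80% power under the 20% missing-data allowance.

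**Working it through.** **Inputs from the documents.** 250 randomized per arm, 1:1 (5.8, 5.8.1); 200 per arm analysable at 20% missing (5.8.1: 250 × 0.80 = 200); two-sided 5%; target power 80%; effects in SD units, so SD = 1.

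**Inputs assumed.** The correlation r between baseline and follow-up scores is not given, so r = 0.3, 0.5 and 0.7 are used. The model is linear with identity link; another link, or a Box-Cox transformation (5.8), may give a different gain.

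**Step 1. Reproduce the plan's figure.** The detectable effect is approximately d = (1.960 + 0.842) × √(2/n). At n = 200 this is 2.802 × 0.100 = 0.280. The noncentral t distribution (398 df) gives 0.281, and 79.8% power at d = 0.28. The figure in 5.8.1 is correct.

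**Step 2. Add the baseline score.** Adjustment multiplies the residual SD, and so the detectable d, by √(1 − r²). At 200 per arm (noncentral t, 397 df):

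| Assumed r | √(1 − r²) | Detectable d, 80% power | Reduction from 0.281 | Power at d = 0.25 |
|---|---|---|---|---|
| none (t-test of 5.8.1) | 1 | 0.281 | – | 70.3% |
| 0.3 | 0.954 | 0.268 | 5% | 74.4% |
| 0.5 | 0.866 | 0.243 | 13% | 82.1% |
| 0.7 | 0.714 | 0.201 | 29% | 93.7% |

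A simulation of 4,000 trials per r at d = 0.25 gave adjusted power of 73.2%, 81.5% and 93.7%, in line with the formula. Power at d = 0.25 with 200 per arm reaches 80% once r is about 0.46.

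**Step 3. Compare with the planned model.** Step 2 starts from the unadjusted t-test, but the planned Aim 2 model already adjusts for smoking status. Suppose, as an illustration only, that smoking status correlates 0.3 with both the baseline and the follow-up score. Smoking adjustment alone then brings the detectable d to 0.281 × √(1 − 0.09) = 0.268. The further gain depends on the partial correlation (r − 0.09)/(1 − 0.09):

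| Assumed r | Partial correlation p | √(1 − p²) | Further reduction in detectable d |
|---|---|---|---|
| 0.3 | 0.21/0.91 = 0.231 | 0.973 | about 3% |
| 0.5 | 0.41/0.91 = 0.451 | 0.893 | about 11% |
| 0.7 | 0.61/0.91 = 0.670 | 0.742 | about 26% |

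If smoking status explained none of the variance, the Step 2 reductions would apply almost unchanged.

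**Step 4. The 0.25 effect, unadjusted t-test.**

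| Missing | Analysed per arm | Power at d = 0.25 | Detectable d, 80% power |
|---|---|---|---|
| 20% | 200 | 70.3% | 0.281 |
| 10% | 225 | 75.4% | 0.265 |
| none | 250 | 79.7% | 0.251 |

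So 0.25 matches the detectable effect only with complete data, which is not the scenario used in that paragraph.

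**The case against.** The strongest reply is that nothing here is an error. The main model adjusts for the stratification factor and is valid under randomization; adding a baseline covariate is a choice. That stands, and the point is made only as an improvement in precision.

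Second, the benefit rests on a correlation that the documents do not give, and at r = 0.3 it is only about 4 percentage points of power at d = 0.25. That also stands. But the cost is one degree of freedom out of about 400 and no new data.

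Third, the comparison in Step 2 flatters the gain because the planned model already contains smoking status. This is right, and Step 3 shows by how much under one assumption.

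Fourth, 5.8.1 states power and the 20% allowance for knowledge and perceived risk only. Using 200 per arm for benefits, barriers and self-efficacy extends that allowance by assumption.

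Fifth, the 0.25 sentence is loose wording right after a correct figure, and 20% is a ceiling. That is fair: 70% is the power at the full allowance, and the wording would not merit comment on its own.

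A reader might infer more than the documents support:

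- That the Aim 2 comparisons are biased. They are not; omitting a baseline covariate in a randomized comparison costs precision.
- That the plan rules out baseline adjustment. It only fails to name it.
- That the attrition sensitivity analysis is faulty. It suits its own purpose.
- That 5.8.1 claims 80% power at 0.25, or that the trial is too small. It makes no such claim, and no sample size rests on 0.25.

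**Conclusion.** The point holds as a free improvement. The main Aim 2 models name smoking status only, while the baseline value of each of the five continuous scores is available before randomization. Relative to the t-test of 5.8.1, naming it would lower the detectable d at 200 per arm by about 5%, 13% or 29% for r = 0.3, 0.5 or 0.7. Relative to the planned smoking-adjusted model the gain is somewhat less if smoking status explains outcome variance (about 3%, 11% or 26% under the Step 3 assumption). These sizes rest on the assumed r and on a linear model. Validity, the primary uptake analysis and the sample size are untouched.

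The 0.25 wording is a true but minor inconsistency. The d = 0.28 statement is right and should stay.

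**What to change.** In section 5.8, Aim 2, add: 'For each continuous outcome, at each follow-up time point at which it is measured, the main between-group model will have the follow-up score as dependent variable and will include arm, smoking status and the baseline value of the same score.' The time point needs naming because 4.1.1 mentions a single follow-up at 6 months, whereas Table 1 in 5.5 shows one at 1 week and the Aim 1 table refers to both. Keep the attrition sensitivity analysis as it is.

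In 5.8.1, either delete the claim that 0.25 is conservative or replace it with: 'In an unadjusted two-sided 5% t-test, power at d=0.25 is about 70% with 20% missing (200 per arm) and about 80% only with no missing data (250 per arm).' Leave the d = 0.28 sentence unchanged.

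The cost is one added sentence and one deleted or corrected sentence, with no new data, no more participants and no change to the primary analysis. The Aim 2 sentence should be in place before outcome data by arm are examined.
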